8.1 Dose Levels for each drug in the combination

	Pembrolizumab (Every 21 days)	Lenalidomide (Days 1-21)	Dexamethasone (Days 1, 8, 15, 22)
Starting dose	200 mg	25 mg	40 mg
-1		15 mg	20 mg
-2		10 mg	12 mg
-3		5 mg	4 mg
-4		Discontinue	Discontinue

Note: If pembrolizumab is discontinued, the patient may continue treatment with the remaining drugs. If lenalidomide is discontinued, patient will go to event monitoring.

8.11 Instruction for initiation of a new cycle of therapy

A new cycle of treatment may begin on the scheduled Day 1 of a new cycle if:

- The ANC is $\geq 1000/\mu\text{L}$
- The platelet count is $\geq 50,000/\mu\text{L}$
- Any other non-hematologic drug-related adverse event that may have occurred has resolved to \leq Grade 1 or baseline severity.

If these conditions are not met on Day 1 of a new cycle, dosing should be delayed for 1 week. At the end of that time, the patient should be re-evaluated to determine whether the criteria have been met. If the patient continues to fail to meet the above-cited criteria, delay therapy and continue to re-evaluate.

If any drug dosing was halted during the previous cycle and was restarted with a one-level dose reduction without requiring an interruption for the remainder of the cycle, then that reduced dose level will be initiated on Day 1 of the new cycle.

If any drug dosing was omitted for the remainder of the previous cycle or if the new cycle is held due to known hematologic toxicity newly encountered on the scheduled Day 1, then the new cycle will be started with a one-level dose reduction. If a new cycle of therapy cannot be restarted within 4 weeks of the scheduled Day 1 due to non-resolution of drug related toxicities, the patient will be removed from protocol therapy and will go to event monitoring.

8.2 Dose modifications for pembrolizumab based on adverse events during a cycle

→ → Use the NCI Common Terminology Criteria for Adverse Events (CTCAE) version 4.0* unless otherwise specified ← ←

CTCAE System/Organ/Class (SOC)	Adverse Event	Omit Pembrolizumab for Grade	Timing for Restarting Pembrolizumab	Pembrolizumab Discontinuation
Gastrointestinal disorders	Diarrhea or Colitis	2-3	AE resolves to Grade 0-1	AE does not resolve within 12 weeks of last dose or inability to reduce corticosteroid to 10 mg or less of prednisone or equivalent per day within 12 weeks
		4	Permanently discontinue pembrolizumab	Permanently discontinue pembrolizumab
Investigations	AST, or ALT, or Blood bilirubin	2	AE resolves to Grade 0-1	AE does not resolve within 12 weeks of last dose.
		3-4	Permanently discontinue pembrolizumab	Permanently discontinue pembrolizumab
Metabolism and nutrition disorders	Glucose intolerance (Type 1 diabetes mellitus [if new onset]) or Hyperglycemia	T1DM or 3-4	Omit pembrolizumab for new onset Type 1 diabetes mellitus or Grade 3-4 hyperglycemia associated with evidence of beta cell failure	Resume pembrolizumab when patients are clinically and metabolically stable.
Endocrine disorders	Endocrine disorders – Other, specify: Hypophysitis	2-4	AE resolves to Grade 0-1. Therapy with pembrolizumab can be continued while endocrine replacement therapy is instituted	AE does not resolve within 12 weeks of last dose or inability to reduce corticosteroid to 10 mg or less of prednisone or equivalent per day within 12 weeks
Endocrine disorders	Hyperthyroidism	3	AE resolves to Grade 0-1	AE does not resolve within 12 weeks of last dose or inability to reduce corticosteroid to 10 mg or less of prednisone or equivalent per day within 12 weeks
		4	Permanently discontinue pembrolizumab	Permanently discontinue pembrolizumab

CTCAE System/Organ/Class (SOC)	Adverse Event	Omit Pembrolizumab for Grade	Timing for Restarting Pembrolizumab	Pembrolizumab Discontinuation
Endocrine disorders	Hypothyroidism		Therapy with pembrolizumab can be continued while thyroid replacement therapy is instituted	Therapy with pembrolizumab can be continued while thyroid replacement therapy is instituted
General disorders and administration site conditions	Infusion related reaction	2 ^a	AE resolves to Grade 0-1	Permanently discontinue pembrolizumab if AE develops despite adequate premedication
		3-4	Permanently discontinue pembrolizumab	Permanently discontinue pembrolizumab
Respiratory, thoracic and mediastinal disorders	Pneumonitis	2	AE resolves to Grade 0-1	AE does not resolve within 12 weeks of last dose or inability to reduce corticosteroid to 10 mg or less of prednisone or equivalent per day within 12 weeks
		3-4	Permanently discontinue pembrolizumab	Permanently discontinue pembrolizumab
Renal and urinary disorders	Acute kidney injury or Chronic kidney disease (e.g. Renal failure or Nephritis)	2	AE resolves to Grade 0-1	AE does not resolve within 12 weeks of last dose or inability to reduce corticosteroid to 10 mg or less of prednisone or equivalent per day within 12 weeks
		3-4	Permanently discontinue pembrolizumab	Permanently discontinue pembrolizumab
	All Other Drug-Related Adverse Events ^b	3 or severe	AE resolves to Grade 0-1	AE does not resolve within 12 weeks of last dose or inability to reduce corticosteroid to 10 mg or less of prednisone or equivalent per day within 12 weeks
		4	Permanently discontinue pembrolizumab	Permanently discontinue pembrolizumab

Note: Permanently discontinue for any severe or Grade 3 (Grade 2 for pneumonitis) drug-related AE that recurs, or any lifethreatening event.

a If symptoms resolve within one hour of stopping drug infusion, the infusion may be restarted at 50% of the original infusion rate (e.g., from 100 mL/hr to 50 mL/hr). Otherwise dosing will be held until symptoms resolve and the subject should be premedicated for the next scheduled dose (Section 9.9f).

b Patients with intolerable or persistent Grade 2 drug-related AE may hold study medication at physician discretion. Permanently discontinue study drug for persistent Grade 2 adverse reactions for which treatment with study drug has been held, that do not recover to Grade 0-1 within 12 weeks of the last dose.

* Located at http://ctep.cancer.gov/protocolDevelopment/electronic_applications.ctc.htm

** Use the following to describe actions in the Action column:

- Omit = The current dose(s) for the specified drug(s) during a cycle is skipped. The patient does not make up the omitted dose(s) at a later time
- Hold/Delay = The current dose(s) of all drugs during a cycle is delayed. The patient does make up the delayed dose(s) when the patient meets the protocol criteria to restart drugs
- Discontinue = The specified drug(s) are totally stopped

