9.8 Diarrhea/Colitis

Subjects should be carefully monitored for signs and symptoms of enterocolitis (such as diarrhea, abdominal pain, blood or mucus in stool, with or without fever) and of bowel perforation (such as peritoneal signs and ileus).

- All subjects who experience diarrhea/colitis should be advised to drink liberal **quantities of clear fluids. If sufficient oral fluid intake is not feasible, fluid and**

electrolytes should be substituted via IV infusion. For Grade 2 or higher diarrhea, consider GI consultation and endoscopy to confirm or rule out colitis.

- For **Grade 2 diarrhea/colitis** that persists greater than 3 days, administer oral corticosteroids.
- For **Grade 3 or 4 diarrhea/colitis** that persists > 1 week, treat with intravenous steroids followed by high dose oral steroids.
- When symptoms improve to Grade 1 or less, steroid taper should be started and continued over no less than 4 weeks.

9.9a Type 1 diabetes mellitus

If new onset, including diabetic ketoacidosis [DKA] or \geq Grade 3 Hyperglycemia, if associated with ketosis (ketonuria) or metabolic acidosis (DKA)

- For **T1DM** or **Grade 3-4** Hyperglycemia
- Insulin replacement therapy is recommended for Type I diabetes mellitus and for Grade 3-4 hyperglycemia associated with metabolic acidosis or ketonuria.
- Evaluate patients with serum glucose and a metabolic panel, urine ketones, glycosylated hemoglobin, and C-peptide.

9.9b Hypophysitis:

- For **Grade 2** events, treat with corticosteroids. When symptoms improve to Grade 1 or less, steroid taper should be started and continued over no less than 4 weeks. Replacement of appropriate hormones may be required as the steroid dose is tapered.
- For **Grade 3-4** events, treat with an initial dose of IV corticosteroids followed by oral corticosteroids. When symptoms improve to Grade 1 or less, steroid taper should be started and continued over no less than 4 weeks. Replacement of appropriate hormones may be required as the steroid dose is tapered.

9.9c Hyperthyroidism or Hypothyroidism:

Thyroid disorders can occur at any time during treatment. Monitor patients for changes in thyroid function (at the start of treatment, periodically during treatment, and as indicated based on clinical evaluation) and for clinical signs and symptoms of thyroid disorders.

- **Grade 2** hyperthyroidism events (and **Grade 2-4** hypothyroidism):

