Grade 2 Requires infusion interruption but responds promptly to symptomatic treatment (e.g., antihistamines, NSAIDS, narcotics, IV fluids); prophylactic medications indicated for <=24 hrs	
Stop Infusion and monitor symptoms. Additional appropriate medical therapy may include but is not limited to: IV fluids Antihistamines NSAIDS Acetaminophen Narcotics
 
Increase monitoring of vital signs as medically indicated until the subject is deemed medically stable in the opinion of the investigator. If symptoms resolve within one hour of stopping drug infusion, the infusion may be restarted at 50% of the original infusion rate (e.g., from 100 mL/hr to 50 mL/hr). Otherwise dosing will be held until symptoms resolve and the subject should be premedicated for the next scheduled dose.
 
Subjects who develop Grade 2 toxicity despite adequate premedication should be permanently discontinued from further trial treatment administration.
	
Subject may be premedicated 1.5h (\pm 30 minutes) prior to infusion of pembrolizumab (MK-3475) with:
 
Diphenhydramine 50 mg po (or equivalent dose of antihistamine)
 
Acetaminophen 500-1000 mg po (or equivalent dose of antipyretic)

NCI CTCAE Grade	Treatment	Premedication at subsequent dosing

Grades 3 or 4
 
Grade 3: Prolonged (i.e., not rapidly responsive to symptomatic medication and/or brief interruption of infusion); recurrence of symptoms following initial improvement; hospitalization indicated for other clinical sequelae (e.g., renal impairment, pulmonary infiltrates)
 
Grade 4: Life-threatening; pressor or ventilatory support indicated
	
Stop Infusion.
 
Additional appropriate medical therapy may include but is not limited to:
 
 IV fluids Antihistamines NSAIDS Acetaminophen Narcotics Oxygen Pressors Corticosteroids Epinephrine 
Increase monitoring of vital signs as medically indicated until the subject is deemed medically stable in the opinion of the investigator. Hospitalization may be indicated.
 
Subject is permanently discontinued from further trial treatment administration.
	
No subsequent dosing

Appropriate resuscitation equipment should be available in the room and a physician readily available during the period of drug administration.
		

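### Section 8.2 lets pembrolizumab restart after hypophysitis or beta-cell-failure diabetes with no Grade 4 exception, while the table's own note requires a permanent stop for any life-threatening event

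*Combined protocol and SAP*

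**What the plan says.** Section 8.2 grades events on a named scale: "Use the NCI Common Terminology Criteria for Adverse Events (CTCAE) version 4.0* unless otherwise specified".

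- **Hypophysitis row** ("Endocrine disorders – Other, specify: Hypophysitis"). The omission column reads 2-4. The restart column reads "AE resolves to Grade 0-1. Therapy with pembrolizumab can be continued while endocrine replacement therapy is instituted". The discontinuation column provides for a permanent stop only if, within 12 weeks, the event has not resolved or corticosteroids cannot be reduced to the stated level.
- **Diabetes/hyperglycemia row.** Its scope is "Omit pembrolizumab for new onset Type 1 diabetes mellitus or Grade 3-4 hyperglycemia associated with evidence of beta cell failure". The instruction that follows is "Resume pembrolizumab when patients are clinically and metabolically stable".
- **Note under the table.** "Permanently discontinue for any severe or Grade 3 (Grade 2 for pneumonitis) drug-related AE that recurs, or any lifethreatening event".

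The key to the table defines omitting as skipping a dose that is not made up later. Section 8.0 makes the modifications strict for the first two cycles and treats them as guidelines after that.

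**The concern.** Both rows expressly include Grade 4 and both lead back to pembrolizumab. The note leads to a permanent stop and exempts no organ system. A site treating a patient whose hypophysitis or new-onset diabetes is life-threatening therefore finds two instructions for the same event in the same table. What is at stake is whether that patient is exposed again to the experimental agent, and whether two sites or two investigators would act alike. In the first two cycles Section 8.0 leaves no room to settle the matter by judgement.

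**Working it through.** No power, significance level or event count enters the main point, so the check is a comparison of texts. The only arithmetic concerns how often the situation could arise.

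1. **Hypophysitis judged life-threatening.** Under the row, Grade 4 lies inside 2-4, so pembrolizumab is omitted and may restart at Grade 0-1. Under the note, it is stopped for good. Both cannot be done.

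2. **Life-threatening event in the diabetes/hyperglycemia row.** Under the row, pembrolizumab resumes once the patient is stable. Under the note, it is stopped for good. The conflict is the same, but only within the row's scope (new-onset type 1 diabetes, or Grade 3-4 hyperglycemia with evidence of beta cell failure). Section 9.9a names diabetic ketoacidosis for this condition, so serious presentations are foreseen.

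3. **Search for a rule of precedence.** Section 8.2 has none. Section 8.0 has a tie-break for several adverse events occurring together, but none for two instructions about one event. For Grade 3-4 hypophysitis, Section 9.9b says "treat with an initial dose of IV corticosteroids followed by oral corticosteroids" and then covers taper and hormone replacement. Section 9.9a covers insulin and work-up. Neither addresses stopping pembrolizumab.

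4. **Comparison with the other rows.** The table has ten rows.
   - Seven stop pembrolizumab permanently at Grade 4: diarrhea/colitis, AST/ALT/bilirubin, hyperthyroidism, infusion reaction, pneumonitis, renal events, and all other drug-related events.
   - Hypothyroidism lists no grade for omission.
   - The two rows at issue are the only ones that include Grade 4 without a Grade 4 stop. A reader cannot tell whether this is a deliberate exception to the note or an omission.

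5. **Wording inside the hypophysitis row.** Grades 2-4 stand in the omission column, which by the table's key means the dose is skipped. The restart cell adds that therapy can go on while replacement is started. The hypothyroidism row uses nearly the same sentence but lists no grade for omission, so it is coherent there. In the hypophysitis row a reader must guess whether it modifies the omission or only the restart.

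6. **Size.** Section 15.17 lists hypophysitis and type 1 diabetes among toxicities below 1%. Section 16.12 gives 37 evaluable patients and at most 41 in all. The upper bound on expected cases, for each event, is rate x patients:
   - 0.01 x 37 = 0.37
   - 0.01 x 41 = 0.41

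   These rates are not split by grade, so the expected number of life-threatening cases is smaller still. No rate is given for Grade 3-4 hyperglycemia with beta cell failure.

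**The case against.** The strongest reply is that a note under a table naturally overlays every row: the row applies unless the event is life-threatening, and then the note applies. That is a possible reading, but the text does not state it. The rows name Grade 4 themselves, and seven other rows repeat the Grade 4 stop in the row instead of leaving it to the note. The opposite reading, that the specific row displaces the general note, is just as open.

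Other parts of the reply do stand, and they limit the point.

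- **Grade 4 and life-threatening are not shown to be identical here.** The wording "Grade 4: Life-threatening; pressor or ventilatory support indicated" is in the infusion-reaction table of Section 9.9f and is printed for that event only. The CTCAE Grade 4 definitions for hypophysitis and hyperglycemia are not in the documents. Section 8.4 describes Grade 3 hyperglycemia partly by a glucose range, so Grade 4 may also be partly a laboratory value. The conflict is certain for an event judged life-threatening, whatever its grade label.
- **A reader might infer that every Grade 4 hyperglycemia is caught, and often, because all patients take dexamethasone.** The documents do not support this. The row requires new-onset type 1 diabetes or evidence of beta cell failure. Other pembrolizumab-related Grade 4 hyperglycemia falls under the all-other row, which agrees with the note. Section 8.0 adjusts each drug by attribution, and hyperglycemia due to dexamethasone has its own rule in Section 8.4.
- **A reader might count three incompatible instructions for hypophysitis.** The cell can be read in sequence: omit, restart at Grade 0-1, and do not let continuing hormone replacement stand in the way. Section 9.9b fits that reading. The wording is unclear, but it is not a proven contradiction.
- **A reader might object that the diabetes row's omit and resume texts stand under the wrong column headings.** That may be an effect of reading the table from PDF, and the meaning is plain either way.
- **A guidance document may bear on this.** Section 10.56 refers to an Appendix 4 on managing immune-related events, which is not in the text available. It could contain a reconciling rule.

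**Conclusion.** The point holds in a narrow form. For a life-threatening event in the hypophysitis row or the beta-cell-failure row, the row and the note of Section 8.2 give instructions that cannot both be followed. No precedence is stated in the available text, and adherence is mandatory in the first two cycles. The hypophysitis row also needs clearer wording for Grades 2-4.

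The effect falls on individual patient safety and consistent conduct, not on inference. At most about 0.4 cases of each listed event are expected among 41 patients, assuming the below-1% rates in Section 15.17 apply to this population. The primary endpoint is not affected: under Section 8.1 a patient who stops pembrolizumab may continue the other drugs, and the evaluability rule in Section 16.311 does not depend on which instruction was followed.

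A reader might also infer that the toxicity results for goal 2.24 would be distorted. The plan does not support that. Section 16.325 tabulates maximum grade by event type and considers relationship to treatment. It specifies no analysis of pembrolizumab discontinuation.

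This should be corrected, but it does not threaten the design.

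**What to change.** Reconcile the hypophysitis row and the diabetes/hyperglycemia row with the note under the Section 8.2 table:

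1. State whether the row or the note governs when an event in either row is Grade 4 or life-threatening, and say whether those two terms are meant to coincide. One general sentence on precedence would also settle any similar question for the hypothyroidism row.
2. Reword the hypophysitis row so that each grade has one action, and make clear whether the hormone-replacement sentence applies to the omission or only to the restart.
3. Check that the guidance cited in Section 10.56 agrees with the result.

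Which rule stands is a clinical decision for the sponsor, and none is proposed here. The cost is an edit to two rows and one note, with no change to sample size, visits or analysis.

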8.0 Dosage Modification Based on Adverse Events

Strictly follow the modifications in this table for the first **two** cycles, until individual treatment tolerance can be ascertained. Individual drugs can be dose reduced as per the table below depending on the adverse event attribution. Thereafter, these modifications should be regarded as guidelines to produce mild-to-moderate, but not debilitating, side effects. If multiple adverse events are seen, administer dose based on greatest reduction required for any single adverse event observed. Reductions apply to treatment given in the preceding cycle and are based on adverse events observed since the prior dose.

ALERT: ADR reporting may be required for some adverse events (See Section 10)

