Nervous System Disorders	Peripheral sensory neuropathy Grade 3	Lenalidomide	Omit lenalidomide dose Follow at least weekly If the event resolves to \leq Grade 1 prior to Day 35, restart lenalidomide at next lower dose level and continue the cycle through Day 35	Omit lenalidomide for the remainder of the cycle. See Section 8.11 Instructions for Initiation of a New Cycle and reduce the dose of lenalidomide by 1 dose level
	Peripheral sensory neuropathy Grade 4	Lenalidomide	Discontinue lenalidomide	Discontinue lenalidomide
Immune system disorders	Allergic reaction Grade 2-3	Lenalidomide	Omit dose Follow at least weekly If the toxicity resolves to \leq Grade 1 prior to Day 35 restart at next lower dose level and continue the cycle until Day 35	Omit lenalidomide for the remainder of the cycle If the adverse event resolves to \leq Grade 1, reduce dose 1 level in next cycle If adverse event recurs, discontinue therapy
	Grade 4	Lenalidomide	Discontinue lenalidomide	Discontinue lenalidomide
Vascular disorders	Thromboembolic event \geq Grade 3	Lenalidomide	Omit dose and start anticoagulation; restart at investigator's discretion (maintain dose level)	Omit lenalidomide for remainder of cycle and start anticoagulation. Maintain dose level in next cycle
Kidney and Urinary System	Renal Insufficiency	Lenalidomide	CrCl $>$ 50 mL/min: No adjustment CrCl 30-50 mL/min: 10 mg/day CrCl $<$ 30 mL/min (no dialysis): 15 mg every 48 hours CrCl $<$ 30 mL/min (dialysis): 5 mg daily (after HD (hemodialysis) on HD days)	

CTCAE System/Organ/Class (SOC)	ADVERSE EVENT	AGENT	ACTION** Days 2-14 of cycle	ACTION** Day \geq 15 of cycle
Endocrine disorders	Hyperthyroidism or Hypothyroidism \geq Grade 2	Lenalidomide	Omit lenalidomide for remainder of cycle, evaluate etiology, and initiate appropriate therapy. See Instructions for Initiation of a New Cycle and reduce the dose of lenalidomide by 1 dose level	Omit lenalidomide for remainder of cycle, evaluate etiology, and initiate appropriate therapy. See Section 8.11 , Instructions for Initiation of a New Cycle and reduce the dose of lenalidomide by 1 dose level

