 - In hyperthyroidism, non-selective beta-blockers (e.g. propranolol) are suggested as initial therapy
 - In hypothyroidism, thyroid hormone replacement therapy, with levothyroxine or liothyronine, is indicated per standard of care
- **Grade 3-4** hyperthyroidism
 - Treat with an initial dose of IV corticosteroid followed by oral corticosteroids. When symptoms improve to Grade 1 or less, steroid taper should be started and continued over no less than 4 weeks. Replacement of appropriate hormones may be required as the steroid dose is tapered.

9.9d Hepatic:

- For **Grade 2** events, monitor liver function tests more frequently until returned to baseline values (consider weekly).
 - Treat with IV or oral corticosteroids
- For **Grade 3-4** events, treat with intravenous corticosteroids for 24 to 48 hours.
- When symptoms improve to Grade 1 or less, a steroid taper should be started and continued over no less than 4 weeks.

9.9e Renal Failure or Nephritis:

- For **Grade 2** events, treat with corticosteroids.
- For **Grade 3-4** events, treat with systemic corticosteroids.
- When symptoms improve to Grade 1 or less, steroid taper should be started and continued over no less than 4 weeks.

9.9f Management of Infusion Reactions:

Signs and symptoms usually develop during or shortly after drug infusion and generally resolve completely within 24 hours of completion of infusion.

Table 9.9e1 below shows treatment guidelines for subjects who experience an infusion reaction associated with administration of pembrolizumab (MK-3475).

Table 9.9e1 Infusion Reaction Treatment Guidelines

NCI CTCAE Grade	Treatment	Premedication at subsequent dosing
Grade 1 Mild reaction; infusion interruption not indicated; intervention not indicated	Increase monitoring of vital signs as medically indicated until the subject is deemed medically stable in the opinion of the investigator	None

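### For drug-related hypothyroidism still above Grade 1 and above baseline on Day 1 of a new cycle, Sections 8.2 and 8.3 expect treatment to go on, but Section 8.11 delays the cycle and, if the event has not resolved within 4 weeks, removes the patient from all protocol therapy

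*Combined protocol and SAP*

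**What the plan says.** Five places bear on drug-related hypothyroidism.

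- **Section 8.2, hypothyroidism row.** The omit-grade cell is empty. The restart column and the discontinuation column carry the same sentence: "Therapy with pembrolizumab can be continued while thyroid replacement therapy is instituted". The row has no resolution grade and no time limit. The Note under the table still stops pembrolizumab permanently for a recurrent severe or Grade 3 drug-related event and for any life-threatening event.
- **Section 9.9c.** For Grade 2-4 hypothyroidism: "In hypothyroidism, thyroid hormone replacement therapy, with levothyroxine or liothyronine, is indicated per standard of care". No drug hold is mentioned.
- **Section 8.3, thyroid row (Grade 2 or higher).** "Omit lenalidomide for remainder of cycle, evaluate etiology, and initiate appropriate therapy". The row then refers to Section 8.11 and lowers lenalidomide by one level.
- **Section 8.11.** One condition for starting a new cycle is: "Any other non-hematologic drug-related adverse event that may have occurred has resolved to" Grade 1 or less, or baseline severity. If it is not met, dosing is delayed and the patient re-evaluated. If a new cycle "cannot be restarted within 4 weeks of the scheduled Day 1 due to non-resolution of drug related toxicities", the patient leaves protocol therapy for event monitoring. No endocrine exception is given.
- **Section 8.0.** The modifications are strict for the first two cycles. "Thereafter, these modifications should be regarded as guidelines".

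**The concern.** Hypothyroidism is a listed pembrolizumab toxicity (Section 15.17, in the 1% to 10% group), so the situation is foreseeable. Section 8.2 does not treat it as a ground for stopping pembrolizumab, and Section 9.9c manages it with replacement. Yet a patient who starts replacement and is still above Grade 1 and above baseline on Day 1 cannot begin the next cycle under Section 8.11, and may lose pembrolizumab, lenalidomide and dexamethasone together 28 days later. An investigator who relies on the Section 8.2 permission departs from Section 8.11. Nothing in the protocol says which section governs, so two investigators could treat the same patient differently and both cite the text.

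**Working it through.** The protocol states no figure on this point, so the check compares the rules and then sets them on the calendar.

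**Step 1: the rules for one patient.** Take drug-related Grade 2 hypothyroidism with no thyroid abnormality at baseline, replacement started, still Grade 2 on Day 1 of a new cycle.

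| Source | Instruction |
|---|---|
| 8.2, hypothyroidism row | Pembrolizumab may go on |
| 9.9c | Give replacement; no hold |
| 8.3, thyroid row | Omit lenalidomide for the rest of the current cycle; next cycle one level lower |
| 8.11, Day 1 | Delay dosing and re-evaluate |
| 8.11, Day 1 + 28 days, still unresolved | Remove from protocol therapy |

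The footnotes to the Section 8 tables define a hold or delay as covering all drugs, so an 8.11 delay also reaches the pembrolizumab that 8.2 allows. The 8.3 row refers to 8.11, so 8.11 plainly applies to this event.

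**Step 2: do the rules meet on the calendar?** Pembrolizumab is given every 21 days and cycles last 28 days (Section 7.1). Four cycles last 4 × 28 = 112 days.

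- Pembrolizumab days: 1, 22, 43, 64, 85, 106 (6 doses).
- Cycle Day 1: study days 1, 29, 57, 85.

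| Blocked Day 1 | Limit (+28) | Pembrolizumab due from the block to the limit | Pembrolizumab lost if removed | Lenalidomide-dexamethasone cycles lost |
|---|---|---|---|---|
| Cycle 2, day 29 | day 57 | day 43 | 43, 64, 85, 106 = 4 of 6 | 3 of 4 |
| Cycle 3, day 57 | day 85 | days 64, 85 | 64, 85, 106 = 3 of 6 | 2 of 4 |
| Cycle 4, day 85 | day 113 | days 85, 106 | 85, 106 = 2 of 6 | 1 of 4 |

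One or two infusions fall due during a 28-day delay: 8.2 permits them and 8.11 delays them. The losses in the last two columns occur only if the event stays above Grade 1 and above baseline for the full 28 days. The cycle 2 row lies clearly within the period that Section 8.0 makes strict. The later rows depend on how far that section softens 8.11.

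**Step 3: how many patients?** Assume that the Section 15.17 range carries over to this combination. Then 37 × 0.01 = 0.37 to 37 × 0.10 = 3.7 of the 37 evaluable patients would be expected to have hypothyroidism. That range is not restricted by grade or time, so it is a ceiling for events of Grade 2 or higher in the first four cycles. After screening, Section 4.1 schedules sTSH only every 6 months, which is longer than 112 days, so early cases would be found mainly through symptoms.

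**The case against.** The strongest reply is that both rules can be obeyed. Section 8.2 concerns events during a cycle, covers one drug, and is permissive. Section 8.11 is a gate for starting the whole combination. An investigator who follows 8.11 breaks no mandatory instruction in 8.2. Section 8.3 is also stricter for lenalidomide and refers to 8.11, and Section 8.1 sends a patient to event monitoring when lenalidomide is discontinued, so regimen-level removal is not alien to the design.

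Part of this stands: 8.2 permits rather than commands. It does not reconcile the sections. The 8.2 permission also fills the discontinuation column, whereas 8.11 can end the drug. Pembrolizumab doses fall due inside an 8.11 delay. And 8.3 foresees a next cycle at a lower dose, not removal.

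Four stronger readings are tempting but are not supported.

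- **Every such patient is removed after 4 weeks.** Removal requires non-resolution for 28 days. Whether a patient on replacement still grades above 1 depends on CTCAE text that is not in the documents. If the grade falls in time, only a delay remains.
- **The conflict is mandatory throughout.** Section 8.0 makes the modifications guidelines after two cycles. It speaks of a table, and 8.11 is not one, so its reach is arguable, but later softening cannot be excluded.
- **The trial loses power.** The Section 16.2 design (stop at 3 or fewer successes in 13; positive at 13 or more in 37) reproduces the stated 0.856 at a true rate of 0.45. If a fraction f were removed before success, the rate would be 0.45(1 − f): f = 0.01 gives 0.4455 and power 0.845; f = 0.10 gives 0.405 and power 0.722. Those values need every listed case to be above Grade 1, early, unresolved for 28 days and before a confirmed VGPR, which is implausible. Removal is not automatically failure either, since note a to Table 11.51 allows confirmation until new therapy starts.
- **Hypophysitis and type 1 diabetes have the same defect.** The hypophysitis row does say "Therapy with pembrolizumab can be continued while endocrine replacement therapy is instituted", but it also has an omit grade (2-4), a resolution grade (0-1) and a 12-week limit. The diabetes row omits pembrolizumab first and then says "Resume pembrolizumab when patients are clinically and metabolically stable".

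**Conclusion.** The inconsistency is real but narrow. It applies to drug-related hypothyroidism above Grade 1 and above baseline on Day 1 of a new cycle. It is mandatory at least in the first two cycles and possibly only guidance afterwards. The certain effect is a delay of all drugs that 8.2 and 9.9c do not call for. Removal from all three drugs follows only if the event stays unresolved for 28 days, and the documents do not show how often that would happen. The stake is the individual patient's treatment, at worst 4 of 6 pembrolizumab doses and 3 of 4 lenalidomide-dexamethasone cycles within the first four. The number affected is likely to be small. The effect on power is probably negligible and is no part of the case for change.

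**What to change.** Add to the third bullet of Section 8.11:

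*Exception: Grade 2-3 hypothyroidism for which thyroid replacement has been started does not prevent a new cycle from starting and does not count toward the 4-week limit. Pembrolizumab follows Section 8.2, including its Note on recurrent Grade 3 and life-threatening events. Lenalidomide restarts one dose level lower per Section 8.3.*

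Leave hypophysitis and type 1 diabetes out: their rows already require omission, and an exemption would need a definition of clinical stability that the protocol does not give. If the team does intend removal, the hypothyroidism row of Section 8.2 should say so instead.

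The cost is one sentence, with no change to visits, drug supply or sample size. The small downside is that some patients restart lenalidomide, at a reduced dose, with hypothyroidism still above Grade 1 on replacement.
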